Before smoking the assigned research cigarette, participants will complete a **cigarette purchase task (CPT)**, a behavioral economics-based measure of cigarette reinforcement, which assesses hypothetical demand for cigarettes across a range of prices, and a **cross-price elasticity purchase task**, which assesses hypothetical demand for experimental cigarettes at increasing prices of an individual's preferred brand of cigarettes. Participants will also complete assessment of nicotine withdrawal and craving prior to smoking using the **Minnesota Nicotine Withdrawal Scale (MNWS)**¹⁵ and the **Questionnaire on Smoking Urges**¹⁶. Heart rate and blood pressure will be taken before smoking (some measurements may not be taken if sessions are completed remotely). After smoking, participants will complete assessments of subjective response to smoking with the **modified Cigarette Evaluation Questionnaire (mCEQ)**, the **Duke Sensory Questionnaire (DSQ)**, and the **Nicotine Drug Effects Questionnaire (NDEQ)**. Participants will also complete the MNWS again.

The **Predicted Behavior Questionnaire** will be asked at the beginning of Visits 3 and 4, prior to when the VLNC is smoked. It asks participants to indicate their intentions to use cigarettes and other tobacco products when cigarettes have lower nicotine content and come menthol or non-menthol flavor. The **Expected Utility Questionnaire** will also be administered at Visits 3 and 4, before participants smoke. This questionnaire asks the degree to which participants would use the study cigarettes they just smoked for the past week (menthol or non-menthol) would help them quitting, be less dangerous than smoking, give up tobacco use, smoker fewer cigarettes, etc.

Participants will report their perceptions of the health risks associated with both their usual brand and their study cigarette brand using the **Perceived Health Risks Assessment**.¹⁷

ECOLOGICAL MOMENTARY ASSESSMENT (EMA)

C.5 EMA Procedure. Participants will record cigarette smoking and alternative tobacco use, craving, symptoms of withdrawal, and subjective ratings (e.g., satisfaction, reward, craving reduction, physical sensations like throat hit) associated with smoking the most recent cigarette in response to 2 random prompts to their phone each day. We will use a mobile EMA application, in which participants answer a set of survey questions on their cell phone by selecting

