Participants will be involved in the study for approximately 2 months. There will be 5 in-person study visits (or virtual sessions) and a total of 21 days of daily monitoring of cigarette smoking behavior. There will be a 30-day follow-up after visit 5, that will be conducted either in person or over the telephone.

4. Describe blinding, including justification for blinding or not blinding the trial.

We considered blinding participants to the nicotine content in the research cigarettes to minimize the possibility that perceptions of these cigarettes may impact ratings of appeal/reinforcement and use behavior (e.g., compensatory behavior). We ultimately chose not blind participants so that we could model real-world conditions in which participants would be aware of the nicotine content of the cigarettes they smoke. [name], our consultant, is taking this same approach (e.g., not blinding participants) in a pilot study conducted as part of her U54. While we know about responses to VLNCs in a blinded scenario, findings from our study will be one of the first to inform VLNC work in an un-blinded scenario with young people.

5. Include justification for inclusion of a placebo or non-treatment group.

N/A. This is not a treatment study.

6. Describe what happens to participants receiving therapy when study ends or if their participation in the study ends prematurely.

N/A. This is not a treatment study.

7. Indicate where the procedures will be completed.

All participant recruitment, enrollment and testing will occur at the research laboratory of the TSET Health Promotion Research Center (HPRC) in Oklahoma City, OK. HPRC has conducted smoking research for the past 5 years.

8. Indicate whether clinically relevant research results, including individual research results, will be disclosed to participants. If so, under what conditions?

Females will be asked to take a pregnancy test at each in-person (or virtual) session prior to smoking, to determine eligibility. If a woman is pregnant, she will be given the results of her test immediately. If the session is completed remotely,

pregnancy tests will be provided to the participant before the session (mailed or curb-side pick-up) and pregnancy will be confirmed prior to beginning a smoking session.

9. Identifiers might be removed and the de-identified information may be used for future research without additional informed consent from the subject.

D. Biospecimens

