Visit 5 (Experimental Tobacco Marketplace)	\$ 50
Bonus for eligible referral	\$20
Bonus for scheduling and attending first visit within 5 days of phone screening	\$20
EMA	

Call completion (*42 calls)	\$1/call (\$42 total)
Bonus for completing all calls each week (* 3 weeks)	\$10/week (\$30 total)
Bonus for completing 85% of calls for 3 weeks	\$45
Total possible EMA	\$117
Research Cigarette Compliance	
Returned used cigarettes	\$7 maximum/week @ 2 weeks
Returned unused cigarettes (\$0.25/cigarette)	\$20 maximum/participant
Returned empty packs (\$1/pack)	\$5 maximum/participant
Total possible cigarette compliance	\$14 + \$20 + \$5 = \$39
30-Day Follow-up	
30-day Follow-Up + ETM 3	\$45
Travel for In Person or Curbside Pick-up/Drop-Off	
\$10 for each in person visit/curbside pick-up/drop-off of study materials @ 4 visits	\$40 maximum/participant
Bonus for completing all phases	\$ 70
Maximum Total	\$ 571

To enhance retention in all phases of the study, due to higher than anticipated loss-to-follow-up, we will offer a bonus of missed incentive amounts to participants who are hard-to-reach or schedule. With this bonus, participants will be eligible to receive missed compensation opportunities, if they complete remaining in-person study sessions and/or surveys. Missed opportunities may include the bonus for scheduling and attending the first visit within 5 days of phone screening (\$20), the eligible referral bonus (\$20), bonuses for completing all EMA surveys each week (\$30 maximum) even if they miss some surveys, bonus for completing 85% of EMA surveys for 3 weeks (\$45) even if they miss some surveys, and the bonus for completing all phases of the study (\$70). Enhancement bonuses will be separated into \$20 increments to encourage a participant to attend any remaining session(s) they have not completed. After the final in person session is complete, the participant will be eligible for all remaining compensation amount not already claimed, up to the maximum of \$571, even if they may not have met the full criteria. Thus, we calculate their maximum bonus amount allotted to participant, and give it to them in \$20 increments (per number of sessions attended). When they complete the final in-person visit, they are eligible for all remaining bonus/compensation to get the maximum amount (\$571).

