Patterns of missing data, compliance, distributional properties of variables, and correlations among all measures will be assessed. We will control for potential variables related to missing data and utilize multiple imputation methods (expectation maximization algorithm).¹⁶⁰⁻¹⁶³ Analysis will use linear mixed modeling with random subjects effects^{164,165} to assess the main effect of cigarette type on the primary and secondary outcomes of interest. Models will use a contrast to compare differences between menthol VLNC and non-menthol VLNC at the day-level on predictions of the outcome of interest and that outcome of interest at time t (e.g., morning) predicting behavior (number of cigarettes, any smoking, craving, withdrawal) occurring at a subsequent time point (controlling for cigarette consumption from the previous report). Comparison of usual brand and the menthol VLNC ratings will also be made to determine the perceived similarity of the VLNC to one's own brand. A sub-group of respondents may have fixed (unchanging) ratings of subjective response, craving, cigarettes per day, or withdrawal over the course of 7 days, although this is unlikely given the team's previous research. We will examine baseline and daily factors that set "no changers" apart from those whose show fluctuations in these factors, and examine these as potential covariates in models. Within-person slopes capturing associations between cigarette type and the EMA outcome of interest will be saved in regression models and used to predict the ETM responses.

4. ETM Analyses (Aim 3)

Primary Outcomes: (a) consumption of alternative tobacco products (milligrams of nicotine for alternative tobacco sources) as a function of cigarette type available. Typically, as cigarette price increases, consumption of other tobacco products increases.¹⁴ Secondary Outcomes: (a) breakpoint: the first price at which consumption of the available cigarette is zero; (b) intensity of demand: consumption at the lowest price); (c) elasticity of demand: sensitivity of cigarette consumption to increases in cost, (d) Omax: maximum expenditure for cigarette type available; and (e) Pmax: price at which expenditure is maximized.

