The analyses for the aim using ETM data will examine the predictive validity of laboratory and EMA data on the ETM outcomes of interest, separately for each cigarette type. Hierarchical linear regression models will predict the ETM outcome of interest, controlling for baseline cigarettes per day, nicotine dependence, other tobacco use, and relevant demographics in Step 1 and then

including the laboratory or EMA-derived slopes of appeal/reinforcement in Step 2. Models will separately examine the effects of laboratory and EMA measurements of appeal/reinforcement on the ETM outcomes of interest.

5. Exploratory Analyses

Differences by age (18-24 vs 25-34), sex, race/ethnicity, alternative tobacco product use, and ETM flavor and product preference. Menthol cigarettes are disproportionately used by women, as well as Black and Hispanic smokers.^{18,166-168} As such, sex and race/ethnicity will be examined as moderators of outcomes, as sample size permits. This allows us to adhere to NIH guidance examining sex as a biological variable. Variation in the use of alternative tobacco products during each 7-day take-home phase will be examined as a possible moderator of the reinforcing effects of the research cigarette to which participants are assigned, as well as an outcome assessment of compensatory tobacco use. Given the popularity of menthol cigarette use in adults aged 26-34 years and alternative tobacco product use in this age group,^{17,169-171} flavor preference by product type (e-cigarettes, little cigars) will be examined as an exploratory outcome from the ETM analyses.

Laboratory and EMA concordance and predictive utility. We will examine the association of laboratory and EMA measurements of appeal/reinforcement and determine whether correlations between these measures differ in magnitude by menthol vs non-menthol use and by VLNC vs usual brand. A weak or non-significant correlation could indicate that these paradigms tap into different dimensions of reinforcement/appeal. We will also compare the utility of laboratory vs EMA outcomes as predictors of ETM outcomes to determine the relative contribution of each measurement paradigm. This would advance theoretical models and facilitate future research by identifying the most relevant aspects of abuse liability that uniquely account for the role of menthol in increasing risk for dependence.

6. Study Timeline.

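### The laboratory-versus-EMA comparison reads unique contribution from one-paradigm models and makes no allowance for one rating set against up to 14

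*Combined protocol and SAP*

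**What the plan says.** Section J.4 (ETM Analyses) describes hierarchical regressions of each ETM outcome. Baseline covariates enter in Step 1, and the laboratory or the EMA slope enters in Step 2. It adds: "Models will separately examine the effects of laboratory and EMA measurements of appeal/reinforcement on the ETM outcomes of interest".

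Section J.3 says where the EMA predictor comes from: "Within-person slopes capturing associations between cigarette type and the EMA outcome of interest will be saved in regression models". For the laboratory, J.2 defines relative reinforcing value as a within-subject difference in ratings between cigarette types.

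Section J.5, under exploratory analyses, adds two uses:

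- Comparison: "We will also compare the utility of laboratory vs EMA outcomes as predictors of ETM outcomes to determine the relative contribution of each measurement paradigm". No model, statistic or test is named.
- Concordance: "A weak or non-significant correlation could indicate that these paradigms tap into different dimensions of reinforcement/appeal". No cut-off for weak is given.

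On the number of ratings, each laboratory smoking session (V2 to V4) has one cigarette and one set of post-smoking questionnaires. EMA ratings are collected "in response to 2 random prompts to their phone each day" (C.5), over "a total of 21 days of daily monitoring of cigarette smoking behavior" (Research Design, item 3). Section J plans no reliability estimate, no correction for attenuation and no analysis with equal numbers of ratings.

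**The concern.** Two separate problems meet in the same comparison.

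The first is about the model. How much one paradigm adds beyond the other can be seen only when both are in the model. Two one-paradigm models give two total associations, which overlap to an unknown degree.

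The second is about measurement. An average of many ratings carries less error than a single rating, and error in a predictor lowers both its R² and its correlation with anything else. A higher R² for EMA, or a modest laboratory-EMA correlation, can therefore arise when both paradigms measure an identical person-level effect. Joint modelling does not cure this.

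At stake is one methodological product of the trial. The Specific Aims section says the proposal will validate measures for later policy studies, and J.5 wants to learn which aspects of abuse liability matter uniquely. A future team could drop the laboratory paradigm, or treat the two as distinct constructs, on the strength of a difference in reliability.

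**Working it through.** **Inputs from the documents.** Two prompts a day over 7 days for each of three cigarette types gives 2 × 7 × 3 = 42 surveys. This reproduces the compensation table's entry, "Call completion (*42 calls". It means up to 14 ratings per type, against one laboratory rating set per type. The table's "Bonus for completing 85% of calls for 3 weeks" is a payment threshold, not a forecast; 85% of 14 is about 12. The analytic n is 100 in section J.1 and 138 in the design overview (172 × 0.8 = 137.6), so both were used.

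**Assumptions (not in the documents).** Both paradigms measure the same person-level menthol effect, with SD 0.4. Prompt residual SD is 1, 11 of 14 prompts are answered, and laboratory residual SD is 0.5 to 1. The latent correlation with the ETM outcome is 0.5, and tests are two-sided at 0.05. Step 1 covariates are ignored.

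**Reliability of the menthol minus non-menthol difference** = effect variance / (effect variance + 2 × residual variance / number of ratings).

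- EMA: 0.16 / (0.16 + 2/11) = 0.47
- Laboratory, SD 1: 0.16 / (0.16 + 2 × 1) = 0.07
- Laboratory, SD 0.5: 0.16 / (0.16 + 2 × 0.25) = 0.24

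**Correlation ceiling** for an identical construct = √(product of reliabilities). √(0.47 × 0.07) is 0.19 with unrounded inputs, and √(0.47 × 0.24) = 0.34. Significance at n = 100 needs 0.197.

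**Simulation, n = 100.** Mean R² is 0.12 for EMA and 0.03 to 0.07 for the laboratory. EMA has the larger R² in about 80 to 96% of trials. The correlation is non-significant in about 6 to 54%. At n = 138 the critical value is 0.167 and that range is from under 2% to 41%.

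**What a joint model changes.** Unique R² for EMA is R²(full) − R²(lab); for the laboratory it is R²(full) − R²(EMA). Subtracting, the gap in unique R² equals R²(EMA) − R²(lab), exactly the gap between the separate models. In simulation the ranking was identical either way (81.2% in both, and 95.4% in both, at the two laboratory SDs). Joint unique R² was 0.08 to 0.11 for EMA and 0.01 to 0.03 for the laboratory. So the joint model gives the right quantity, but with the reliability effect still inside it.

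**Second parameterisation.** Let k be the reliability of a single-rating difference, equal in both paradigms. EMA reliability with 14 ratings is 14k/(1 + 13k). The expected R² ratio is that figure divided by k, and the ceiling is √(k × EMA reliability).

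| k | EMA reliability | R² ratio, EMA to lab | Correlation ceiling |
|---|---|---|---|
| 0.2 | 0.78 | 3.9 | 0.39 |
| 0.3 | 0.86 | 2.9 | 0.51 |
| 0.5 | 0.93 | 1.9 | 0.68 |
| 0.7 | 0.97 | 1.4 | 0.82 |

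At k = 0.3 the ratio is 2.8 with 12 ratings and 2.5 with 7. With latent correlation 0.3 or 0.5, EMA ranks first in 78 to 98% of runs at n = 100 and 82 to 99% at n = 138. With one rating each, the ratio is 1.00 and the ranking is even. A non-significant correlation at n = 100 occurs in about 30% of runs at k = 0.1, about 1.5% at k = 0.2, and practically never from k = 0.3 upward.

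**Stable EMA-specific error.** Adding an EMA error that does not average out, with SD 0.3 to 0.5 on the difference, to the first set of assumptions lowers EMA's first-place share to about 55 to 91%. Applying SD 0.5 to each cigarette week lowers it to 40 to 73%.

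**The case against.** A reader might infer that the separate models cause EMA to rank first, that EMA is bound to win, and that the paradigms are bound to look different. The documents support none of these.

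- Separate models do not produce the ranking; the identity above shows that a joint model leaves the order unchanged. The J.4 sentence is about the predictive validity of each paradigm, while the comparison sits in J.5, which leaves its method open and does not rule out a joint model.
- The size depends on reliabilities the documents do not give. A single laboratory rating with reliability 0.78, 0.86 or 0.93 would match 14 EMA ratings with k of 0.2, 0.3 or 0.5. Stable EMA-specific error is plausible: EMA rates the most recent cigarette, use of non-study cigarettes is expected, and some-day smokers are eligible.
- On the plan's non-significance criterion, the correlation would usually be significant unless single-rating reliability is low. The plan's wording is also hedged.
- Averaging over occasions is part of what EMA is for. If the question is which paradigm, as deployed, better predicts purchasing, its reliability is a genuine advantage.

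All four stand and limit the claim. They do not answer the rest. J.5 offers a weak correlation as an alternative criterion with no cut-off, and a ceiling of 0.39 to 0.51 for one and the same construct could be called weak. The paradigms also differ in state, since laboratory ratings follow more than 12 hours of abstinence and EMA ratings do not. And J.5 speaks of relative contribution when the only model written down holds one paradigm at a time.

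**Conclusion.** The point holds in limited form. As written, the plan supplies no model from which unique contribution can be read, and its concordance rule ignores a 14-to-1 difference in the number of ratings. Under comparable per-rating error and a shared construct, EMA tends to rank first in roughly 80 to 96% of trials on the assumptions stated, falling to about 55 to 91% with moderate stable EMA error and lower still with more. A correlation well below 1 is to be expected, somewhere between 0.19 and 0.82 across the assumptions tried.

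The direction follows from the design if per-rating error is comparable; the size rests on assumed reliabilities. It would be wrong to conclude that the result is predetermined. Severity is minor to moderate: the paradigm comparison is exploratory, and the Aim 1 and Aim 2 cigarette contrasts are untouched.

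**What to change.** Only the analysis plan needs to change:

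1. In Step 2, add a model holding both slopes. Report each one's increment in R² over the other, with a bootstrap interval for the difference. Resample participants and re-estimate the slopes in each resample, so that their estimation error is carried through.
2. Report the reliability of the EMA slope. Show the laboratory-EMA correlation beside its reliability ceiling over a stated range of assumed laboratory reliabilities. One session per cigarette type yields internal consistency only, so test-retest error cannot be estimated within the trial and a fully corrected correlation is out of reach.
3. Add a sensitivity analysis using one randomly drawn EMA rating per cigarette type, repeated over draws. Label it as a per-rating question, distinct from how the paradigms perform as deployed. It need not come out even: with prompt SD 1 and laboratory SD 0.5 the reliabilities would be 0.07 and 0.24, favouring the laboratory.
4. Remove the inference of different dimensions from a weak or non-significant correlation alone, and note the difference in abstinence state when interpreting it.

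The cost is extra analysis time, wider intervals and a more cautious conclusion. No new data or visits are needed.

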Aim 1: Determine the influence of menthol flavoring on smoking reinforcement in the context of a reduced nicotine standard in the laboratory. Abstinent smokers (> 12 hours) will attend four laboratory visits. Following a 7-day baseline period of usual brand smoking at home, smoking session 1 will measure reinforcement of one's usual brand cigarette via ad-libitum smoking, where subjective response (satisfaction, craving reduction, psychological reward, sensory effects like throat hit), smoking exposure (CO boost), and behavior (number of puffs, puff volume) will be measured. Following smoking session 1, participants will then undergo two experimental conditions (counterbalanced) in their home environment and the lab for 7 days each: (1) 7 days smoking menthol VLNCs; (2) 7 days smoking non-menthol VLNCs. Participants will be instructed to switch their usual cigarette for the assigned cigarette for each 7-day period (allowing for other product use during that time without specific instruction to model real world behavior). Each condition will be separated by a 7-day wash-out period. On the last day of each condition (smoking Visits 2 and 3), participants will smoke the assigned research cigarette in the laboratory, and data on subjective response, smoking exposure, and behavior will be measured. Hypothesis: Craving reduction and positive subjective response will be greater for menthol VLNCs compared to non-menthol VLNCs, but lower compared to usual brand.

Aim 2: Determine the influence of menthol flavoring on smoking reinforcement in the context of a reduced nicotine standard in the natural environment. During each 7-day period of exposure, participants will complete assessments of cigarette and other tobacco use, withdrawal, and subjective response (satisfaction, craving reduction, reward, sensory effects) via twice-daily EMA. Hypothesis: Cigarettes per day, craving reduction, and positive subjective response will be greater for menthol versus non-menthol VLNCs, but lower compared to usual brand. Per previous work, ATP use will be greater in both VLNC conditions compared to usual brand. Effects of menthol vs non-menthol VLNCs on withdrawal, mood, cigarette compliance, and ATP will be compared.

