After smoking their preferred/usual brand in their home environment for 7-days (baseline period) and then in the laboratory ad libitum, participants will undergo two experimental conditions of smoking SPECTRUM menthol and non-menthol very low nicotine cigarettes (VLNCs) (order of administration counterbalanced) in their home environment for 7 days and then in the lab ad libitum. The experimental phases of smoking research VLNCs will be separated by a 7-day wash-out period, where participants will be asked to resume the same amount of smoking as the baseline period. On the last day of each experimental condition, 12-hour abstinent participants will smoke the assigned research cigarette in the laboratory, where data on toxicant exposure (i.e., boost in exhaled carbon monoxide) and smoking topography measures will be collected. Participants will also complete questionnaires about smoking urges, withdrawal, mood, and subjective effects of smoking (satisfaction, psychological reward, sensory effects) immediately before and after smoking a cigarette at each visit. Participants will be compensated \$35 for the baseline session or \$25 if they are deemed ineligible. Participants will be compensated \$45 for laboratory smoking sessions 2-4 if they are eligible and \$50 for session 5. Participants can receive a \$20 bonus incentive if they schedule and attend the first study session with 5 business days of completing the phone screener.

During each 7-day take-home period of smoking SPECTRUM cigarettes, participants will be instructed to switch their usual brand cigarette for the assigned research cigarette and will provide daily data on cigarette use, withdrawal, smoking urge, other tobacco use, and subjective response to smoking via twice daily EMA, as well as other factors related to tobacco use.

Protocol Modifications in Response to COVID-19

To prioritize the participants' and the study team's health, the sequence of study requirements may vary due to COVID-19, rules and guidelines set by authorities at the National, Local, or University level. This may mean that the in-person study visits may become virtual (e.g. online video calls) visits. Per our other IRB approved protocols (10581, 10974), the consent and baseline survey will be collected electronically if a participant chooses virtual sessions. Age will be verified before participants engage in their first smoking session if they complete the study remotely/virtually.

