At the end of V2, participants will receive the first set of assigned research cigarettes and will be asked to smoke those cigarettes in their home environment for 7 days; starting on the day after V2. The ordering of flavor of the research VLNCs to be smoked (menthol and non-menthol) will be counterbalanced and assigned prior to Visit 2 (Individuals who complete the session remotely will be scheduled for a pick-up date to get the VLNCs1). During each 7-day period of exposure, participants will be instructed to switch their usual brand cigarette for the assigned research cigarette and will provide daily data on smoking quantity, craving, withdrawal, subjective response, and alternative tobacco product use via twice daily EMA surveys. We will allow for other tobacco product use without specific instruction to align with the real-world scenario, as these products will exist on the market even if a menthol ban and/or a reduced nicotine standard are enacted. Given the high prevalence of dual and poly-tobacco use in this age group, we will examine change in alternative tobacco product use between conditions as a secondary outcome in exploratory analyses, per Co-I [name]'s and [name]'s previous work. Participants will have a 7-day period wash-out period of return to smoking as usual (own brand of cigarette) between the experimental conditions.

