Primary Outcomes: (a) The relative reinforcing value (RRV) of usual brand cigarettes vs menthol VLNCs; (b) RRV of non-menthol VLNCs vs menthol VLNCs. RRV will be operationalized as within-subject differences in subjective ratings of cigarette appeal/reinforcement (satisfaction, reward, craving reduction, physical sensations) during each ad libitum smoking session. Secondary Outcomes: (a) CO boost; and (b) puff topography (number of menthol versus non-menthol cigarette puffs consumed, number of minutes smoked, interval between puffs).

Analysis of covariance will be conducted to examine effects of cigarette type (usual brand, menthol VLNC, non-menthol VLNC) on the outcomes of interest, controlling for cigarettes per day (CPD), nicotine dependence, race/ethnicity, gender, and age of smoking onset as potential covariates. Factors related to study drop-out and differences in cigarette compliance will also be examined as potential covariates. Exploratory analyses will examine differential reactions to usual brand and each research cigarette by race/ethnicity (White, Black, Hispanic, Other) and by gender. Significant interactions will be followed up with individual contrasts of cell means using Fisher's Least Significant Difference tests. We will examine whether topography differs as a function of in-person versus remote session.

3. EMA Analyses (Aim 2)

Primary Outcomes: (a) within-day subjective response (craving reduction, satisfaction, psychological reward, physical sensations like throat grab) to the most recent cigarette smoked; (b) within-day number of research cigarettes smoked per day; (c) within-day number of non-research cigarettes smoked; and (d) within-day withdrawal intensity. Secondary Outcomes: (a) within-day use of alternative tobacco products; (b) changes over the course of days (creating an average change score for each person) for each outcome; (c) number of days abstinent from tobacco use.

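### J.5 uses alternative tobacco use during the VLNC weeks to moderate the cigarette effect, although the plan also treats that use as an outcome of the cigarette; a pre-exposure measure should be named instead

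*Combined protocol and SAP*

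**What the plan says.** Section J.5 states that ATP use, measured in each take-home week, "will be examined as a possible moderator of the reinforcing effects of the research cigarette". The same sentence adds a second use of the variable: "as well as an outcome assessment of compensatory tobacco use".

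The description of the take-home period places it after exposure starts: "During each 7-day take-home period of smoking SPECTRUM cigarettes, participants will be instructed to switch their usual brand cigarette for the assigned research cigarette". The first research cigarettes are handed out at the end of V2.

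Elsewhere ATP use is an outcome of cigarette condition:

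- Aim 2 (section A) hypothesises that "ATP use will be greater in both VLNC conditions compared to usual brand". For the two research cigarettes it gives no direction: "Effects of menthol vs non-menthol VLNCs on withdrawal, mood, cigarette compliance, and ATP will be compared".
- J.3 lists "Secondary Outcomes: (a) within-day use of alternative tobacco products".
- The V2 section says "we will examine change in alternative tobacco product use between conditions as a secondary outcome in exploratory analyses".

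The plan also collects ATP use before any research cigarette is dispensed. The sources are the twice-daily EMA in the usual-brand week (Pre-Screening/Baseline Session), the baseline survey, and the timeline follow-back at V2 (Measures Descriptions). J.5 does not name any of these as the moderator. It also gives no model for a moderator that the exposure can change.

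**The concern.** A moderator should be fixed before the exposure whose effect it modifies. Here the proposed moderator can respond to that exposure. Someone who finds a given cigarette unsatisfying may turn to other products that week, as the plan's word compensatory suggests. Grouping people by that week's ATP use then partly sorts them by their reaction to the cigarette, and the effect will appear to differ between groups even if it is the same for everyone.

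What is at stake is one exploratory finding, but a policy-relevant one. The design deliberately leaves ATPs available to imitate a real market. A report that ATP use alters menthol's appeal could be read as effect modification when it only reflects the association between liking a cigarette and using substitutes.

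**Working it through.** The plan gives no figure to reproduce, so this is a check of structure followed by an illustration.

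**Model.** Let Y be the rating, A the ATP use in the same week, and c = 1 for one VLNC and 0 for the other. With a person effect, Y = α + βc + γA + δcA. Moderation is δ. The within-person difference is

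D = Y1 − Y0 = β + γ(A1 − A0) + δA1.

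**Assumptions (none from the documents).** Rating variance is 1 with within-person correlation 0.5. The cigarette effect is purely additive, so δ = 0. ATP use = person level + mean shift of 0.5 in one condition − k × rating + noise, with variance 1 and between-week correlation 0.5 before the link is added. The link k runs from 0 to 0.5. Tests are two-sided at 0.05, with 4,000 runs per setting. The protocol gives two analytic sample sizes, 100 (J.1) and 138 (C.4), so both are used.

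**Why one week's value misleads.** Cov(D, A1) = −k(1 − 0.5) = −0.5k and Var(A1) = 1 + k². The expected slope of D on A1 is −0.5k/(1 + k²). At k = 0.5 this is −0.25/1.25 = −0.20, and the simulation gives −0.20. The slope is non-zero although δ = 0.

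**Why both weeks' values help only partly.** If k is the same for both cigarettes, the coefficients on A1 and A0 are equal and opposite, so the estimate of δ (their sum) is zero. If the link exists for one cigarette only, the sum is −0.25k/(1 + k² − 0.25). At k = 0.5 this is −0.125/1.00 = −0.125, which the simulation also gives.

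**False-interaction rates (%), n = 100 / n = 138**

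| k | One week's ATP, equal link | Both weeks, equal link | Both weeks, link in one condition only | Pre-exposure ATP, equal link |
|---|---|---|---|---|
| 0.1 | 8.8 / 8.8 | 5.0 / 4.6 | 6.1 / 6.8 | 5.3 / 5.2 |
| 0.2 | 16.2 / 20.7 | 5.6 / 4.9 | 9.3 / 10.2 | 5.1 / 5.1 |
| 0.3 | 29.6 / 40.5 | 5.1 / 5.2 | 13.4 / 14.6 | 5.1 / 4.8 |
| 0.5 | 61.1 / 76.6 | 5.2 / 4.8 | 19.3 / 26.4 | 4.3 / 4.4 |

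- With a mean shift in ATP use and no link (k = 0), every version stays at about 5% (4.5 to 4.7).
- With an equal link and a floor on ATP use, the both-weeks model reaches 5.2 to 10.4%.
- Across all settings, one week's ATP use gives about 8 to 77% and pre-exposure ATP use 4 to 6%.

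A separate simulation gives the same ordering: about 15 to 93% for one week's value, 4 to 9% for both weeks with an equal link, 9 to 45% when the link differs between cigarettes, and about 5% for baseline ATP use.

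**The case against.** **The natural model may be sound.** J.5 speaks of each take-home week, and J.3 uses linear mixed models. Week-specific ATP use interacted with cigarette type is a fair reading, and the table shows it is close to nominal when the link is equal. This stands as a limit on the size of the problem. It does not remove it, because J.5 names no model and nothing shows that the link is equal for the two cigarettes.

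**The plan's hypothesis is not the mechanism.** Aim 2 predicts more ATP use on either VLNC than on usual brand, and a mean shift alone does no harm. For menthol against non-menthol no direction is stated. That dislike drives ATP use is therefore an assumption. A reader might infer that any apparent moderation must be reverse causation, but the documents do not support that. The laboratory ratings come at the end of each week, so most of that week's ATP use precedes them.

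**The between-week change looks far worse.** A reader who regresses the rating difference on the change in ATP use would see rejection in 22 to 98% of trials under assumed links and might call that false moderation. It is not. With δ = 0, that regression estimates γ, the within-person association between ATP use and rating, which the simulation contains by construction. It says nothing about an interaction and should not be used as a measure of the problem.

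**Baseline ATP use asks a different question.** It asks whether existing ATP users respond differently, not whether using ATPs alongside a VLNC alters its appeal. This is correct, and it is a reason to keep the concurrent association as a descriptive result. The opening of J.5 also lists differences by ATP use in general, so a baseline version is not excluded; it is only not named.

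**Conclusion.** The point holds as a risk in an exploratory analysis. J.5 gives one post-exposure variable two roles, moderator and outcome. If ATP use responds to how well the cigarette is liked, the moderation test can mislead. Error is well above 5% if one week's ATP use is the moderator or if the link differs between the two cigarettes. It is close to 5% if both weeks' values are modelled and the link is equal. All these rates rest on assumed link strengths and scales, since the documents supply none. The documents do not show that false moderation will occur, nor how large it would be. The primary contrasts, the sample size and the safety rules do not depend on this analysis, so severity is low.

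**What to change.** In J.5:

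1. Name pre-exposure ATP use as the moderator, from either the usual-brand-week EMA or the V2 timeline follow-back, and say which. Wash-out-week use is not a substitute, because by then each participant has already used one research cigarette.
2. Keep take-home-week ATP use as an outcome.
3. If its concurrent association with ratings is reported, use week-specific values for both conditions and label the result descriptive, not effect modification.

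The cost is a sentence or two, with no new data. The price is the narrower question that baseline use answers, which item 3 partly offsets.
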